5.3.2 Submitting an Expedited Safety Report to the Local IRB

Once the medical monitor receives all supporting documentation for the reported event, the Medical Monitor will determine if the safety report is eligible for expedited review. The medical monitor will log the initial event within 1 day after initial receipt. The Medical Monitor will complete the review of the event and will create a MedWatch form. This form, as well as other supporting documentation, will be forwarded to the Medical Monitor for review. The Medical Monitor will finalize the report for distribution within 2 days after initial receipt. When expedited safety reporting to regulatory authorities is indeed required, the Investigator should review and update any newly available materials at once.

Each expedited safety report will routinely include a brief cover memorandum, the completed MedWatch Form FDA 3500A, and any additional pertinent information recommended by the sponsor, or study Medical Monitor. Once the report is assembled, the Principal Investigator must submit the expedited safety report to the local IRB within the required reporting timeframe. Follow-up reports should be submitted when requested or when pertinent information becomes available.

5.3.3 Submitting Adverse Events Report to IRBs

When the Principal Investigator receives an expedited safety report from the medical monitor or the sponsor detailing adverse events occurring under this protocol or in other studies using the same test article, it must be promptly submitted to the site's IRB. The Principal Investigator must retain a copy of such reports as submitted to their IRB.

5.3.4 Contacting the Medical Monitor

When contacting the medical monitor, the protocol number and location of the study should be clearly noted. If necessary, back-up personnel and procedures are in place to assure adverse events are adequately handled and reported correctly. Neurotech Safety contact is provided on the protocol cover page.

5.4 Obligations of Study Sponsor

Neurotech is the IND holder with the FDA and hence is the legal sponsor of this study. The protocol was designed by the sponsor in collaboration with participating study investigators.

Neurotech must immediately investigate each reported adverse event. The sponsor has 15 days to submit a report to the FDA of any reported adverse experience that is associated with the use of the test article that is both serious and unexpected.

5.5 Adverse Events Defined

An adverse event includes any unfavorable and unintended sign (including a clinically significant abnormal laboratory finding), symptom, or disease temporally associated with the use of the medicinal product, whether or not related to the investigational product or device.

Medical conditions or diseases present before a participant starts study treatment are only considered adverse events if they worsen after the participant starts study treatment (temporal association).

For adverse events that result in persistent or significant disability/incapacity, disability/incapacity refers to a substantial disruption of a participant's ability to carry out normal life functions.

Non-serious adverse events that are expected according to previous experience with the test article (as described in the protocol, investigator's brochure and consent materials) can be collected in a routine manner using case report forms. If an expected event is observed to occur during the study at a greater frequency or severity than previously described, it may become an unexpected event that requires further investigation and reporting as an unexpected adverse event. Serious or unexpected adverse events, or any other events not specifically listed on case report forms as expected events, must be promptly reported to the Medical Monitor as noted above. This permits immediate investigation by the Medical Monitor and sponsor to determine the reporting requirements to regulatory authorities.

A hospitalization that is scheduled prior to enrollment for an elective or cosmetic procedure, that is unrelated to the medical condition under study, or is for a procedure scheduled under this protocol, is excluded from this definition of an adverse event.

5.5.1 Serious Adverse Events Defined

A serious adverse event (SAE) [may also be termed a Serious Suspected Adverse Drug Reaction – Serious SADR; or in device studies, a serious unanticipated device effect – Serious UADE] is defined for this protocol as an adverse event or experience that meets one or more of the following criteria:

- A. A death occurring during the study or which comes to the attention of the Investigator within 6 months of the end of the protocol-defined follow-up period, whether considered treatment-related.
- B. A life-threatening event.
- C. An adverse event requiring in-patient hospitalization or prolonged hospitalization due to the adverse event.
- D. An adverse event resulting in a significant, persistent, or permanent change, impairment, damage or disruption in the participant's body function or structure, physical activities or quality of life. As part of the outcome-measure of these studies, any progression in disease will be identified through routine scheduled visual assessments. Natural progression of disease alone (e.g., worsening of vision) is not to be considered a serious adverse event (SAE). Any disease progression that is deemed by the Investigator as beyond the natural progression of disease will be reported as an SAE.
- E. A congenital anomaly or birth defect, where exposure to the test articles prior to conception or during pregnancy is suspected in resulting in an adverse outcome in the child.
- F. An event that otherwise required a medical or surgical intervention to preclude permanent impairment or damage (excluding unrelated elective or cosmetic procedures).

Hospitalization scheduled before a participant enrolls in the study is not the result of a treatment-emergent AE, and therefore events leading to such hospitalization will not be considered study

AEs or SAEs. During the study, if a participant has elective surgery for a pre-existing condition and the condition did not worsen during the study, the reason for elective surgery (and resulting hospitalization, if applicable) should not be considered or reported as an SAE. Surgery or hospitalization should always be reported as an outcome of an adverse event. In the case of surgery for a pre-existing condition, the surgery or hospitalization itself does not merit an SAE report.

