Secondary Endpoints(s):	Secondary efficacy variables will include: mean change from baseline value in Humphrey Visual Field Sensitivity (VFS) from baseline to 24 months, mean change in “5-point” VFS from baseline to 24 months (using the 5 retinal points with greatest average change), mean change from baseline in Best Corrected Visual Acuity (BCVA) at 12, 18, 24, 30 and 36 months, and changes in ERG, Optical Coherence Tomography (OCT), clinical grades of inflammation (anterior chamber cell and vitreous haze grades), and vision-related quality of life (NEI-VFQ25) at each visit.
Safety Endpoint(s):	Safety variables will include the incidence of adverse events, changes in vital signs, marked changes in clinical laboratory data, ECG abnormalities, and findings during physical examinations through 36 months
# of Clinical Sites:	This is a single investigator study; Retinal Degenerations Clinic at the University of California, San Francisco
# of Study Subjects:	Approximately 30
Inclusion Criteria:	
1. Participant must be between 18 and 55 years of age.2. Participant must have a diagnosis of retinitis pigmentosa or Usher syndrome type 2 or 3.3. Participant must understand and sign the protocol informed consent. If the participant’s vision is impaired to the point where he/she cannot read the informed consent document, the document will be read to the participant in its entirety.4. Best-corrected visual acuity must be no worse than 20/63 (at least 59 letters).5. Participants must have clear natural lenses.6. Participants must have less than 6 diopters myopia.7. Participants must be medically able to undergo ophthalmic surgery for the NT-501 device insertion and able to undergo all assessments and tests associated with the protocol.

8. Females of childbearing potential (women with last menses \leq 1 year prior to screening) must agree to use an effective form of birth control from study onset until they complete the study.
9. Participants must have reproducible baseline AOSLO image montages at 2 baseline imaging sessions with quality suitable to identify a minimum of 7 regions of interest (ROIs) at which reliable cone spacing and/or density measures can be made over the central 5.7 degrees.
10. Participants must have interocular symmetry of disease severity as measured by cone spacing, with a difference of less than 2 standard deviations in average cone spacing z-scores at the selected ROIs between the 2 eyes.

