- Peri-implant fibrosis, which either blocks the visual axis of the implanted eye or affects the lens or retina (minor/moderate fibrosis around the implant and/or the attachment point is an expected possibility and will be considered safe on ocular function). Attention should focus on fibrosis that may detach the retina.
- Development of choroidal neovascularization (CNV) in the implanted eye, in which case it may be considered a safety event and explant will be considered.

- Adverse events affecting ocular function, which are different from those expected in the normal course of RP or Usher Syndrome, which are thought to be potentially related to the implant.
- Local or systemic toxicities considered serious adverse events that are potentially related to the implant.

There are risks associated with the surgeries to implant and explant the device and with the sham surgery. In general, the risks of intra-ocular surgery are very small. Some side effects could occur locally in the eye and could affect the participant's vision. There may be pain or infection, a small amount of bleeding, cataract, vitritis, and/or mild astigmatism. A retinal detachment could also possibly occur. Participants may experience a transient red eye from superficial bleeding and itching or a foreign body sensation in the corner of the eye from irritation of the suture itself. These side effects are usually temporary and generally clear up in two weeks or less. In many cases, topical antibiotics and topical steroids can treat minor degrees of inflammation or infection. More serious infection or inflammation may require further surgery on the eye, likely with removal of the implant.

In addition, all adverse events will be collected regardless of severity or potential relationship to the implant, CNTF, or surgical procedure.

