- Adaptive Optics Scanning Laser Ophthalmoscopy (AOSLO): AOSLO will be performed to image each eye of each subject at 2 baseline imaging sessions separated by no more than 1 month. During the first baseline session 37 fixation points will be imaged, each with a 1.2 degree field size, to yield a 5.7-degree diameter, roughly circular, montage of the central retina. The montage will be analyzed over the subsequent 2-3 weeks. Regions of interest (ROIs) in which unambiguous cone mosaics can be identified will be pre-specified in each eye, with the goal to identify at least 1 ROI per degree within 2.85 degrees radius of the anatomic fovea. Requirements for enrollment include the following:
 - At least 7 ROIs must be present in each eye of each patient,
 - ROIs must be located at similar distances from the fovea in each eye
 - There must be less than 2 standard deviations difference between average cone spacing z-scores (standard deviations from the mean at the eccentricity of the ROI) between the 2 eyes.
 - Cone spacing will be quantified in the ROIs by 3 independent graders, all of whom will remain fully masked to the treatment assignment throughout the duration of the study. A second baseline session performed within 1 month of the first session will focus exclusively on the ROIs identified at baseline visit 1. After at least 7 ROIs at 1 degree intervals within 2.85 degrees radius of the fovea in each eye have been identified on 2 baseline visits, the subject is eligible to enroll in the study. The PI will review AOSLO montages from each eye of each subject after each session to ensure the imaging features are indistinguishable before and after surgery between eyes randomized to receive CNTF and sham treatment. Although the PI will not be masked to treatment since she will be examining eyes post-operatively, the Co-Investigator and all study personnel responsible for AOSLO image processing and analysis will remain fully masked to

randomization and treatment assignment throughout the trial.

- Spectral Domain Optical Coherence Tomography (SD-OCT, 20 degree horizontal and vertical scans plus 20 x 15 degree volume scans; Spectralis HRA+OCT, Heidelberg Instruments, Inc.)
- Infrared Fundus photographs (Spectralis HRA+OCT, Heidelberg Instruments, Inc.)

4. Laboratory tests including:

- Serum chemistry
- Hematology with CBC, PTT, and APT
- Urine pregnancy tests (females of childbearing age or potential only)
- Urinalysis
- HIV test

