5.5.3 Relatedness of Event to Test Article or Procedure

The Investigator (or an authorized study physician) must submit an attribution for the relatedness of the reported adverse event to the test article or procedure.

The attribution should take into account both the temporal association and any known physical, physiological or toxicological information regarding the test article that could reasonably infer causality. Relatedness should only be considered for the experimental test article and not for any standard study examination or diagnostic procedures. The five attribution categories are:

- Definite—*Clearly related* to test article or procedure.
- Probable—*Likely related* to test article or procedure.
- Possible—*May be related* to test article or procedure.
- Remotely—*Unlikely related* to test article or procedure.
- Unrelated—*Clearly NOT related* to test article or procedure.

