7.7.2.2 Pooled adverse events

Adverse events will be analyzed according to four main categories:

- Proportion of subjects with *any ocular adverse event*
- Proportion of subjects with *any serious ocular adverse event*
- Proportion of subjects with *any non-ocular serious adverse event*
- Proportion of subjects with *any non-ocular adverse event*

The proportion of subjects with these events will be compared between the arms using Fisher's Exact Test. Poisson regression will be applied to compare the rates of overall adverse events, including recurrent events.

8 Reporting conventions

- All tables and data listings will be presented in landscape orientation, unless presented as part of the text of the final report.
- Figures will be presented in landscape orientation, unless the information is substantially easier to interpret in portrait orientation.
- Direct annotation of figures will be preferred to legends. All figures with more than one variable or item will contain either direct annotation or legends. All annotation will be unambiguously identifiable as such.
- Color will be used in figures only when needed to enhance clarity of communication. All color schemes will be evaluated for visual clarity for individuals with diminished color vision. All color encodings will be identified. Redundant encodings (such as the use of different plot symbols or line dash patterns) will be used in addition to color, so that all figures are interpretable after monochrome reproduction at 100 dots per inch. All dash patterns and line widths will be adequate to be distinguishable after monochrome reproduction at 100 dots per inch. Any distinction between plot symbols (circles, filled circles, diamonds, etc.) will remain clear after monochrome reproduction at 100 dots per inch.

- Sans serif fonts will be used for all labeling (Helvetica, Arial, Futura, or Computer Modern Sans Serif (CMSS)).
- Boldface and italics will not be used unless substantial value is added.
- Decorative fonts and enhancements, including borders and shading, will not be used. Decorative presentation methods, such as ribbon graphs, will never be used.
- All information given in figures will also be presented in summary tables (perhaps only included in an Appendix or in supplementary materials).
- Only standard characters will be used in tables and data listings.

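### Whether vision loss in an eye is labelled serious rests on the judgement of an unmasked investigator, and no by-eye count of large losses from masked measurements is planned alongside that label

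*Protocol*

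**What the plan says.** **The rule.** Protocol 5.5.1 item D covers adverse events that cause lasting impairment. Natural progression on its own, with worsening of vision as the example, is not an SAE. The exception reads: "Any disease progression that is deemed by the Investigator as beyond the natural progression of disease will be reported as an SAE". No change in letters, decibels or between-eye difference is attached to that decision.

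**Who decides.** The Protocol Summary says "This is a single investigator study". Protocol 4.7, in the AOSLO paragraph, says "Although the PI will not be masked to treatment since she will be examining eyes post-operatively". Protocol 4.8 masks participants, vision examiners and AOSLO graders, but gives the progression decision to no masked person. Relatedness is handled similarly in 5.5.3: "The Investigator (or an authorized study physician) must submit an attribution for the relatedness", with no masking condition.

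**Where the label is used.** SAP 7.7.2.2 compares the proportion with "any serious ocular adverse event" between arms. SAP 6.2.3 names serious adverse events among the endpoints examined for harm.

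**What runs in parallel.** Protocol 5.5 treats a pre-existing condition as an adverse event if it worsens after treatment starts. Protocol 4.1 and 5.2 collect all adverse events whatever their severity or cause. SAP 7.7 compares adverse events between eyes by McNemar's test. SAP 7.5.2 compares acuity, field and foveal sensitivity between eyes and describes the results as relevant to safety.

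**The concern.** Loss of vision in the treated eye is a central harm to look for with an intraocular implant. Under item D, the same measured loss could be labelled serious in one eye and natural in the other, by someone who knows which eye holds the implant. Caution about the device could lead to over-calling in the implant eye. Confidence in it could lead to under-calling. Either would distort the serious ocular event comparison.

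The judgement is also unnecessary for that comparison. The fellow eye has the same disease, had to be similar at baseline (inclusion criterion 10), had sham surgery and serves as the control (Protocol 4.4). Natural progression is therefore observed within each person.

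**Working it through.** The documents give no rate of marked vision loss, no classification threshold and no power for a safety comparison, so there is no plan figure to reproduce. All rates and counts below are assumptions unless a source is given.

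**1. What relabelling does to a paired test.** For b discordant pairs that all point the same way, the exact two-sided McNemar p is 2 × (1/2)^b.
- Six implant-eye-only losses, none sham-only: 2 × (1/2)^6 = 0.031.
- Three of the six called natural progression: 2 × (1/2)^3 = 0.25.

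**2. Range under assumed labelling.** Let each eye lose vision markedly with probability p, independently. Let the loss be labelled serious with probability c1 in the implant eye and c0 in the sham eye. The spurious risk difference is p × (c1 − c0). The number of pairs is 20 (the randomization list in SAP 3.3) or 30 (Protocol 4). The true risk is equal in both eyes, with p from 0.2 to 0.4. The last two columns give the probability that exact McNemar rejects at two-sided 0.05.

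| c1, c0 | Spurious difference | 20 pairs | 30 pairs |
|---|---|---|---|
| 0.5, 0.5 | 0 | 0.3% to 1.4% | 1.0% to 2.2% |
| 0.8, 0.5 | +0.06 to +0.12 | 1.6% to 6.5% | 4.1% to 11.1% |
| 0.2, 0.5 | −0.06 to −0.12 | 0.5% to 5.7% | 2.6% to 14.2% |
| 0.8, 0.2 | +0.12 to +0.24 | 4.5% to 29% | 15% to 52% |

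The opposite case is a real difference, 0.4 in implant eyes against 0.2 in sham eyes.
- Even labelling at 0.8 gives serious-event rates of 0.4 × 0.8 = 0.32 and 0.2 × 0.8 = 0.16. McNemar rejects in 11.1% (20 pairs) or 20.0% (30 pairs).
- Labelling only 0.4 of implant-eye losses gives 0.4 × 0.4 = 0.16 against 0.16. Rejection falls to 1.0% or 1.9%.

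Moderate bias moves the test only a little. Strong bias moves it a good deal.

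**3. Whether the masked acuity analysis fills the gap.** SAP 7.5.2.1 applies the rank-test template of 7.5.1.1 to the between-eye acuity difference, with Holm correction for six tests. SAP 3.2 gives a between-eye SD of 0.05 logMAR at baseline and assumes independence of changes, so the SD of the change in difference is 0.05 × √2 = 0.071. I simulated 20 participants, some losing an assumed 0.3 logMAR in the implant eye only, and tested the differences with a signed-rank test, the usual rank test for paired differences.
- Six affected: rejected in 49% of runs at 0.05, and 16% at the first Holm step (0.05/6 = 0.0083).
- Four affected: about 22% and 5%.

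A by-eye count would not be much more powerful for very small numbers: 4 v 0 gives 2 × (1/2)^4 = 0.125. Its value is that it displays the affected eyes, which a mean or rank contrast does not, and that it does so free of the investigator's label.

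**The case against.** The strongest reply is that the documents hold several routes around this judgement, and most of that reply stands.

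- **A reader might infer that vision loss called natural drops out of the safety data.** The documents do not support this. Item D governs seriousness only. Under Protocol 5.5, 4.1 and 5.2 the worsening can still be recorded as an adverse event, and it would then enter the McNemar comparison in SAP 7.7 and the any-ocular-event category in 7.7.2.2.
- **A reader might infer that the SMC would see only the affected counts.** SAP 6.2.2 puts study outcomes in its reports. SAP 6.2.3 lists acuity, cone measures and visual sensitivity as separate harm endpoints.
- **A reader might infer that Protocol 4.1 builds in the same judgement.** Its item reads "Adverse events affecting ocular function, which are different from those expected in the normal course of RP or Usher Syndrome". That is also without a criterion, but it is one item in a list, does not assign the decision to the Investigator, and is followed by the statement that all events are collected.
- Much of the serious ocular category does not depend on this decision. SAP 7.7.2.1 lists events such as retinal detachment, infection and corneal abrasion, and items C and F of 5.5.1 bring in hospitalization and intervention.
- The illustrations rest on assumed counts and labelling rates. An investigator who sees large loss confined to the implant eye, in patients enrolled for symmetry, may well not call it natural.

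What the reply leaves standing is that the label itself is subjective, is made by an unmasked person and feeds a prespecified comparison. Nothing planned counts large losses by eye without it.

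**Conclusion.** The concern holds for the serious or non-serious label for vision loss, and for the serious ocular event comparison that uses it. It does not extend to the masked acuity, field and AOSLO contrasts or to the SMC's review of them. The direction of any bias cannot be read from the documents, and its size is unknown. The 6 v 0 against 3 v 0 example and the table show what is possible under stated assumptions and are not estimates.

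The conclusion assumes that the Investigator in item D is in practice the unmasked PI. That follows from the single-investigator statement and Protocol 4.7. Protocol 4.8 names only the surgeon as unmasked, so the two sections should be reconciled. The gap is modest, but a better measure is available from data already scheduled, so the change is worth making.

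**What to change.** Leave Protocol 5.5.1 and regulatory SAE reporting as they are. In SAP 7.7.2 add a by-eye safety variable:

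- **Definition:** loss from baseline beyond a prespecified cut-off in BCVA, and separately in Humphrey visual field sensitivity.
- **Source:** only scheduled measurements by masked examiners. Acuity taken by the clinical coordinator for safety, which Protocol 4.8 exempts from the masking restriction, is not used.
- **Counting:** both eyes, by the same rule, whatever the presumed cause and whatever the SAE label.
- **Analysis:** exact McNemar test on the eye pairs, with the discordant counts shown.
- **Cut-off:** an analysis definition only, with no bearing on care. It is fixed and documented before anyone choosing it has seen outcome data by eye. No value is proposed here.

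The cost is one derived variable per measure from data already collected, and a short SAP paragraph. The downside is small: some natural progression will be counted, but under the same rule in both eyes.
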